7.8.3. Exploratory Endpoints and Analysis

Unless otherwise specified, the analysis of exploratory endpoints will be performed in pediatric subjects using the ITT Population; the analysis will be repeated for all subjects; if the PP Population is sufficiently different from the ITT Population by more than 5% of study subjects, the analysis may be repeated for pediatric subjects in the PP Population.

7.8.3.1. Characterizing Response in Multiple Food Allergies

Descriptive statistics will be provided for the following for each treatment group:

- Number and percent of subjects with 1 or more qualifying FAs who tolerate the 600-mg level of majority of the Qualifying Foods without dose-limiting symptoms at the Exit DBPCFC
- Number and percent of subjects with 1 or more qualifying FAs who tolerate the 1000-mg level of majority of the Qualifying Foods without dose-limiting symptoms at the Exit DBPCFC
- Number and percent of subjects with 1 or more qualifying FAs who tolerate the 600-mg level of all of the Qualifying Foods without dose-limiting symptoms at the Exit DBPCFC
- Number and percent of subjects with 1 or more qualifying FAs who tolerate the 1000-mg level of all of the Qualifying Foods without dose-limiting symptoms at the Exit DBPCFC

The summaries above will also be present by the number of qualifying FAs.

Figures will be provided to display the endpoints above by treatment group.

7.8.3.2. Maximum Tolerated Dose (MTD)

Qualifying Food Allergies (FAs)

For the MTD in qualifying FAs, the following imputation will apply to the endpoints:

- Subjects who do not undergo the Exit DBPCFC have the MTD for the Exit DBPCFC imputed as the MTD at the Screening DBPCFC for the subjects' individual qualifying FAs.
- In order to calculate fold increase of the MTD at the Exit DBPCFC relative to the Screening DBPCFC, if subjects do not tolerate any dose level they will be assigned an MTD of 1 mg.

The following categorical endpoints will be summarized by frequency and percentages of subjects achieving the endpoint for each treatment group.

- Each level of MTD achieved for each qualifying FA at Screening and Exit DBPCFC
- Each level of the relative (fold) increase in MTD from Screening DBPCFC to Exit DBPCFC for each qualifying FA

- Number and percent of subjects with the Exit DBPCFC MTD greater than the Screening DBPCFC MTD for each ADP101 food source based on subjects with corresponding qualifying food allergies
- Number and percent of subjects with the Exit DBPCFC MTD greater than the Screening DBPCFC MTD for at least one food in each ADP101 food/food group (peanut, tree nut, milk, soy, wheat, sesame, finfish, shrimp, and egg) based on subjects with corresponding qualifying food allergies.

The following endpoints will be provided descriptively (median, first and third quartiles [Q1:Q3], min and max) by treatment group.

- Actual value and fold change of MTD between the screening DBPCFC and the Exit DBPCFC of each individual qualifying FA
- Actual value and fold change of the eliciting dose between the screening DBPCFC and the Exit DBPCFC of each individual qualifying FA

Box plot will be provided for MTDs and eliciting doses at the Screening and Exit DBPCFCs across qualifying FAs.

Non-Qualifying Reactive Food Allergies

For non-qualifying reactive FAs, if both screening and exit DBPCFC results are present, the fold increase in MTD from Screening DBPCFC to Exit DBPCFC for that non-qualifying reactive food will be summarized using both continuous and categorical descriptive statistics as described above for qualifying reactive foods.

Similar summary will be provided for eliciting dose.

Box plot will be provided for MTDs and eliciting doses at the Screening and Exit DBPCFCs across non-qualifying reactive FAs.

7.8.3.3. Neo-Sensitization

Neo-sensitization is defined as subjects who develop confirmed new FAs to previously Non-reactive Foods at Screening, as demonstrated by the Exit DBPCFC.

To determine which subjects would have Exit DBPCFCs on FAs non-reactive at screening, see [Figure 4](#).

The number and percentages of subjects who meet neo-sensitization criteria at any dose level will be summarized by treatment group. As appropriate, the proportions of subjects with neo-sensitization in each ADP101 group versus the pooled placebo group will be compared using the Fisher's exact test. The p-values will be provided. For each food source, the number and percentages of subjects with neo-sensitization at each dose level may be provided as well. The plot of subjects with neo-sensitization at any dose level for any food will be provided.

7.8.3.4. Biomarkers for Each Food Allergy

Serum samples to measure sIgE and sIgG4 for each food, total IgE and total IgG4 will be collected prior to the Screening DBPCFCs, Week 20 and Week 38 (prior to the Exit DBPCFCs). The specific and total IgE/IgG4 and IgG4/IgE ratios will be calculated, listed by subject, and summarized by visit and treatment group. Analyses will be performed on pediatric subjects in the ITT Population and PP Population by treatment group. The analysis will be repeated for all subjects by treatment group.

Results outside the limits of quantification will be displayed as less than the lower limit of quantification (LLOQ), or greater than the upper limit of quantification (ULOQ), as appropriate. These values will be summarized as either the LLOQ or the ULOQ. If the IgE or IgG4 is outside of the limits of quantification, the IgE/IgG4 or IgG4/IgE ratio will be set as missing.

Summary statistics, including mean, SD, geometric mean and geometric coefficient of variation (CV), median, min and max, will be presented for actual values and change from baseline, by time point and treatment group for each biomarker. The sIgE, sIgG4, and their ratios will be summarized for qualifying and non-qualifying reactive foods, as well as non-reactive foods. The graphs of mean (SD) actual value and change from baseline in each biomarker over time will be provided.

Biomarker results will be listed.

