6.2.4. Baseline and Change from Baseline

Unless otherwise specified, the baseline value is defined as the last non-missing value prior to the first dose of study drug.

Change from baseline is defined as the difference between the post-baseline assessment value and the baseline value, i.e., Post-baseline Assessment Value – Baseline Value.

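### The geometric mean and geometric CV planned for biomarker change from baseline are not computable, because change is defined as a difference that can be zero or negative

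*SAP*

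**What the plan says.** SAP 7.8.3.4 gives one list of summary statistics for sIgE, sIgG4, total IgE, total IgG4 and their ratios, reported per visit and per arm. It begins with mean and SD and goes on: "geometric mean and geometric coefficient of variation (CV), median, min and max, will be presented for actual values and change from baseline". Both directions of the ratio are included: "The specific and total IgE/IgG4 and IgG4/IgE ratios will be calculated, listed by subject, and summarized by visit and treatment group". The specific markers and their ratios "will be summarized for qualifying and non-qualifying reactive foods, as well as non-reactive foods".

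SAP 6.2.4 fixes what change means: "Change from baseline is defined as the difference between the post-baseline assessment value and the baseline value", written out as "Post-baseline Assessment Value – Baseline Value". SAP 7.8.3.4 gives no other definition. It mentions no log transformation or ratio to baseline, does not limit the geometric statistics to actual values, and has no rule for zero or negative values.

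For results outside the quantification limits, SAP 7.8.3.4 says: "These values will be summarized as either the LLOQ or the ULOQ". A ratio with either component outside the limits is set to missing.

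Where the SAP wants a ratio scale it says so. SAP 7.8.3.2 plans "Actual value and fold change of MTD between the screening DBPCFC and the Exit DBPCFC of each individual qualifying FA".

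**The concern.** A geometric mean is the exponential of a mean of logs, so it exists only when every value is positive. Actual biomarker values meet that condition, but differences from baseline need not. The SAP therefore asks for a statistic that does not exist for much of the data it will meet, and does not say what to do instead.

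Change in food-allergy biomarkers is a listed exploratory endpoint (SAP 4.4). A blank cell would lose little. The worse outcome is a procedure that takes logs, discards the non-positive changes and prints a number. That number would describe only subjects whose marker rose, and would be positive whatever the treatment did.

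**Working it through.** The plan gives no figure to reproduce here; the check is of definitions, followed by an illustration.

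**Formulas.** Geometric mean = exp(mean[ln x]). Geometric CV = sqrt(exp(var[ln x]) − 1). Both need every x > 0. The planned x is post − baseline (SAP 6.2.4).

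**When x ≤ 0.**
- *The marker falls:* x < 0.
- *Raw sIgE, sIgG4, total IgE or total IgG4 beyond the same limit at both visits:* both values equal that limit, so x = 0. This does not apply to the ratios, which are then missing.
- *Ratios:* if IgE/IgG4 goes from a to b with b > a > 0, its reciprocal goes from 1/a to 1/b, and 1/b < 1/a. A rise in one is a fall in the other, so every subject with a non-zero change has a negative change in one of the two ratios.

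**Five-subject example (assumed values, LLOQ taken as 0.1).** Baseline 0.1, 0.1, 5, 20, 50; post 0.1, 0.1, 2, 25, 30.
- Changes: 0, 0, −3, +5, −20. A log exists for 1 of 5.
- Geometric mean over all five: undefined. Over positive values only: +5.0. One value gives no variance, so there is no geometric CV either.
- Arithmetic mean change: −18/5 = −3.6.
- Geometric mean ratio to baseline: (1 × 1 × 0.4 × 1.25 × 0.6)^(1/5) = 0.30^(1/5) = 0.79, from all five subjects.

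**If non-positive changes were dropped.** The documents give no biomarker distribution, so all inputs are assumptions: log-normal baseline with median 10 and between-subject log-SD 1.3, an independent fold change r with true geometric mean f and within-subject log-SD s, and no censoring at the limits.
- Share dropped = Φ(−ln f / s). For f = 0.60 and s = 0.5: Φ(0.511/0.5) = Φ(1.02) = 84.7%.
- Geometric mean of what is left = 10 × exp(E[ln(r − 1) | r > 1]). It scales with the assumed median and does not depend on the between-subject SD.

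| s | f = 0.60: dropped | f = 0.60: geometric mean of the rest | f = 1.00: dropped | f = 1.00: geometric mean of the rest |
|---|---|---|---|---|
| 0.2 | 99.5% | +0.4 | 50% | +1.1 |
| 0.3 | 95.6% | +0.8 | 50% | +1.8 |
| 0.5 | 84.7% | +1.8 | 50% | +3.3 |
| 0.8 | 73.8% | +4.0 | 50% | +6.0 |

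For a marker that doubles (f = 2.00), only 0% to 19% would be dropped over the same range, so the distortion is much smaller.

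**How often the statistic would be defined.** With 20 subjects, the planned paediatric number in each active arm, and no true change, the chance that all 20 changes are positive is 0.5^20, about one in a million. A separate simulation with doubling (between-subject log-SD 1.2) found all 20 positive in 80% of arms at within-subject log-SD 0.3 and in 7% at 0.6.

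**The case against.** The strongest reply is that the harmful case is not in the plan. A reader might infer that the SAP would report a fall in sIgE as a rise, or show a rise in an unchanged placebo arm. The SAP does not support that. It has no rule for dropping non-positive values, and the programming specifications and table shells are separate documents (SAP 11 and 12). The cell might simply be left blank. This stands: the distorted figures above are conditional.

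Even on that branch, other statistics in the table would expose the problem. For a 40% fall with s = 0.5, the +1.8 would sit beside a median change of about −2.75 and an arithmetic mean change of about −7.5. With no true change the median is about 0. This stands too.

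It is also tempting to say that almost nothing useful is left on change. That overstates the loss. Minimum and maximum are planned alongside mean, SD and median. Geometric means of actual values by visit are planned and valid. With complete pairs, dividing the Week 38 geometric mean by the Screening one gives the ratio to baseline. In the five-subject example, 15^(1/5) / 50^(1/5) = 1.72 / 2.19 = 0.79. Missing visits break the identity, but the information is largely recoverable.

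Nor are the planned graphs an error: "The graphs of mean (SD) actual value and change from baseline in each biomarker over time will be provided" is an acceptable display, and a log axis is a preference.

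One could argue that the geometric statistics were meant for actual values only, or that change meant fold change. The text says neither, and the explicit fold change for MTD in SAP 7.8.3.2 counts against assuming it here.

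**Conclusion.** The point holds as a specification error. Under SAP 6.2.4 and 7.8.3.4 read together, the geometric mean and geometric CV of change are undefined in any cell containing a subject whose marker fell or did not move. For the paired ratios, every non-zero change is negative in one direction or the other. This part needs no distributional assumption.

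The size of any distortion does need assumptions. It rests on the log-normal model and baseline median above, and on software dropping non-positive values. Under those, a true 40% fall would lose 74% to 99.5% of subjects and show about +0.4 to +4.0, and no true change would lose 50% and show about +1.1 to +6.0.

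The consequence is limited. The biomarker endpoints are exploratory and summarised descriptively, and SAP 7.8.3.4 plans no test on them. The primary and secondary endpoints are unaffected. Mean, SD, median, minimum and maximum of change, and the geometric statistics of actual values, all remain valid.

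**What to change.** In SAP 7.8.3.4:
- Restrict the geometric mean and geometric CV to actual values.
- For change, report the geometric mean ratio to baseline, exp(mean[ln post − ln baseline]), with its geometric CV, by visit and treatment group.
- Keep mean, SD, median, minimum and maximum for the absolute change.

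The ratio is defined for every subject with positive values at both visits. A subject at the same limit at both visits contributes a ratio of 1. The result for IgG4/IgE is the reciprocal of that for IgE/IgG4, so the two tables would agree. Confidence intervals (95%) and log-axis plots are optional.

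The cost is wording in the SAP and the table shells. No new samples or data are needed.

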7.8.3.5. Skin-Prick Test

The SPT data for all 15 food sources will be collected prior to the Screening DBPCFCs, Week 38 or at the Early Termination (ET) visit. Analyses will be performed on pediatric subjects in the ITT Population and PP Population by treatment group. The analysis will be repeated for all subjects by treatment group.

Actual values and change from baseline of SPT mean wheal diameter (relative to negative control) will be summarized at all time points for qualifying and non-qualifying reactive foods as well as non-reactive foods using descriptive statistics. The graphs of mean (SD) value and change from baseline in SPT mean wheal diameter (relative to negative control) over time will be provided.

The number and percentage of subjects with a mean wheal diameter ≤ 3 mm or > 3 mm will be presented for each food source and each timepoint.

SPT results will also be listed.

7.8.3.6. Use of Epinephrine as a Rescue Medication

Per protocol, subjects have ready access to 2 nonexpired epinephrine autoinjector (EAI) devices at all times during the study. Epinephrine use as a rescue medication for AEs will be identified from the concomitant medication dataset as medications with a preferred name of

“EPINEPHRINE” indicated as a rescue medication on the concomitant medication eCRF, and reported as adverse event of special interest (AESI) in the AE eCRF.

The number and percent of subjects using epinephrine as a rescue medication for AEs at the Screening and Exit DBPCFCs, and the Pre-Maintenance, Maintenance and EOT will be summarized by treatment group. The number and percent of subjects using epinephrine as a rescue medication by number of epinephrine uses per subject (1, 2, 3, 4, and 5 or more) will be provided as well. Multiple uses per day per subject will be considered a single use. For the Pre-Maintenance, Maintenance and EOT, the number and percent of subjects using epinephrine as a rescue medication will be presented by the event prompting epinephrine use (e.g., accidental exposure, and study drug related), and the maximum severity of AEs prompting epinephrine use will be summarized.

The subjects with epinephrine use at the Screening and Exit DBPCFCs will be plotted by treatment group. The plot of subjects with epinephrine use at the Screening and Exit DBPCFCs by number of epinephrine uses per subject will be provided as well.

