7.1.2. Individual Stopping Rules

Individual stopping rules related to study drug dosing are the following:

- Four or more consecutive missed days on at least 4 occasions due to noncompliance
- > 7 consecutive days of missed dosing due to noncompliance
- Life-threatening anaphylaxis resulting in severe hypotension, defined as systolic blood pressure (BP) below the fifth percentile for age (Banker, 2016), neurological compromise, oxygen saturation < 92%, or mechanical ventilation secondary to study drug dosing or any food challenge

• Nonresponse to 3 or more doses of epinephrine for treatment of a single dose-related allergic reaction

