be extended to up to 8 weeks if a subject requires > 6 food challenges), it is considered a single visit per the study design. The visit and date corresponding to this portion will be taken directly as the Week 40 visit and date from the Suvoda IRT system for dosing dataset or the Week 40 visit from other data domains. The end date will be the date of the last Exit DBPCFC. During the Exit Food Challenge/Week 40 Visit period, the subject will keep taking their maintenance level of study drug except on days when it is specifically withheld for study procedures. For occurrence datasets such as adverse events and concomitant medications, the events or medications recorded with the start dates that falls into the start and end dates of this period, will be classified into this period. If the duration of these events span multiple periods, they will be considered ongoing safety events.

Adverse events during the Exit Food Challenge/Week 40 Visit period may be summarized by two periods: (a) Exit DBPCFC during challenge, i.e., days when Exit DBPCFC tests were administered and (b) Exit DBPCFC off challenge, i.e., days when Exit DBPCFC tests were not administered, in order to differentiate potentially treatment emergent vs potentially DBPCPC procedure-related event rates.

- **EOT:** This portion commences immediately after the Week 40 visit (the last Exit DBPCFC). Per the schedule of assessments, it covers an additional up to 4 weeks of daily blinded treatment after the last Exit DBPCFC until the subject completes treatment through the EOT visit. Although this portion spans over an up to 4 week period, it is considered a single visit per the study design. The visit and date corresponding to this portion will be taken directly as the EOT visit and date from either the Suvoda IRT system for doing dataset, or the EOT visit from other data domains. For occurrence datasets such as adverse events and concomitant medications, a start date of the last Exit DBPCFC plus 1 day and an end date using EOT eCRF date will be used to classify data into this portion. If the duration of these events span multiple periods, they will be considered ongoing safety events.

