7.6. Medications

Medications will be coded using the World Health Organization Drug Dictionary (WHODrug) B3 September 2020 version or later.

Subject incidence will be tabulated by Anatomic Therapeutic Class (ATC) level 2 and preferred term (PT), by treatment group and overall using the Safety Population. Subjects will be counted only once for each ATC level 2 or PT if they have multiple records of the same ATC or PT in the database. The incidences will be presented by ATC in descending order for the total column and then, within an ATC, by PT in descending order for the total column.

Medications detailed below will be summarized separately using the Safety Population.

All medications will be presented in by-subject data listings.

Prior and Concomitant Medications

Prior medication is defined as any medication received prior to the beginning of screening. Concomitant medication is defined as any medication continued or newly received at or after the beginning of screening. If a prior medication continues on or after screening, this prior medication will also be a concomitant medication.

Prior medications and concomitant medications will be summarized by treatment group.

Rescue Medications

For allergic reactions to food allergens that may occur during the DBPCFCs, subjects will be treated with epinephrine at the discretion of the investigator. Treatment of allergic reactions during the DBPCFCs, study drug dosing, and SPT may also require antihistamines, IV fluids, beta-adrenergic agonist (e.g., albuterol), oxygen, corticosteroids, and/or epinephrine, as indicated. Rescue medications will be identified by Yes responses to the Rescue Medication Question on the prior and concomitant medications source data.

These rescue medications will be summarized using the Safety Population. Rescue medications will also be summarized for Screening, Pre-Maintenance, Maintenance, Exit Food Challenge/Week 40 Visit, and Follow-Up Period.

Concomitant Procedures and/or Non-drug Therapies

Concomitant procedures and/or non-drug therapies will be coded using MedDRA version 23.0 or later. All concomitant procedures and/or non-drug therapies data will be presented in a by-subject listing using the Safety Population.

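### The epinephrine table counts days with use, not doses, and does not place dosing-related use between Exit challenges; the by-period rescue table omits EOT

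*SAP*

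**What the plan says.** SAP 7.8.3.6 tabulates subjects by number of epinephrine uses (1 up to 5 or more) and plots the same count for the Screening and Exit challenges. The counting rule is: "Multiple uses per day per subject will be considered a single use".

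On periods, the same section says that subjects using epinephrine "for AEs at the Screening and Exit DBPCFCs, and the Pre-Maintenance, Maintenance and EOT will be summarized by treatment group". A second breakdown covers fewer periods: "For the Pre-Maintenance, Maintenance and EOT, the number and percent of subjects using epinephrine" as rescue "will be presented by the event prompting epinephrine use (e.g., accidental exposure, and study drug related", together with the maximum severity of the AEs that prompted the use.

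For rescue medication in general, SAP 7.6 says: "Rescue medications will also be summarized for Screening, Pre-Maintenance, Maintenance, Exit Food Challenge/Week 40 Visit, and Follow-Up Period". It also plans a summary not restricted by period, and by-subject listings of all medications.

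SAP 3.1 and 6.4.3 keep subjects on daily study drug through the Exit period. The dose is withheld on challenge days, with further days possible at the investigator's judgment. Up to 4 more weeks of blinded dosing follow, before the EOT visit. For AEs only, SAP 6.4.3 defines two parts of the Exit period, challenge days and "Exit DBPCFC off challenge, i.e., days when Exit DBPCFC tests were not administered", so that drug-related and challenge-related events can be told apart. SAP 7.9 says some AE summaries will use this split.

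Protocol 7.1.2 lists among the individual stopping rules: "Nonresponse to 3 or more doses of epinephrine for treatment of a single dose-related allergic reaction".

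**The concern.** ADP101 is in its first clinical study, and safety and tolerability are a stated objective. Epinephrine use is one of the plainest descriptive measures of how hard a reaction was to control. Protocol 2.3.2 cites systemic reactions needing epinephrine in 7.7% on active and 3.4% on placebo during maintenance in a licensed peanut immunotherapy program. If that pattern carries over, dosing-related epinephrine that has no row would fall more on ADP101 than on placebo.

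Three features matter:

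- **Doses within a reaction.** The protocol treats this quantity as informative. The stopping rule above uses it, and Protocol 8.3.2 uses it when it says that one or two intramuscular injections ordinarily do not amount to intensive therapy. The planned uses table cannot show it.
- **Off-challenge Exit days.** Subjects take study drug at home on these days. The only epinephrine table that reports use by cause does not cover them.
- **EOT in SAP 7.6.** Up to 4 weeks of blinded dosing are missing from the by-period rescue list.

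**Working it through.** The plan gives no figure to reproduce here. The check sets the period lists side by side and sizes the windows.

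**1. Same-day rule.** Take subject A with one injection, subject B with three injections in one reaction on one day, and subject C with one injection on each of three days. A and B both count as 1 use and C counts as 3, so the table orders subjects by days with use. All three are subjects with any use under either count, so that number does not change. At the challenges, a subject's plotted count cannot exceed the number of challenge days.

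As an illustration, if a share q of epinephrine days has k extra doses, the share of doses not counted is kq/(1 + kq). The documents give no q, so q from 5% to 30% is an assumption:

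- k = 1: 0.05/1.05 = 4.8% to 0.30/1.30 = 23.1%
- k = 2: 0.10/1.10 = 9.1% to 0.60/1.60 = 37.5%

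**2. Period lists.**

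| Portion of treatment | Study drug taken | 7.8.3.6, any use | 7.8.3.6, by cause and severity | 7.6, by period |
|---|---|---|---|---|
| Pre-Maintenance | yes | yes | yes | yes |
| Maintenance | yes | yes | yes | yes |
| Exit, challenge days | withheld | yes | no | yes, one Exit block |
| Exit, off-challenge days | yes, unless further withheld | not named | no | yes, one Exit block |
| EOT | yes | yes | yes | no |

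Two separate gaps result. Off-challenge Exit days are unplaced in 7.8.3.6 and undivided in 7.6. EOT is missing only from 7.6. SAP 7.7 (exposure), 7.8.3.6 and 7.9 all name EOT, which suggests an oversight in 7.6.

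**3. Size of the windows.** Inputs from SAP 6.2.3: 40 weeks, then up to 6 weeks of Exit challenges (8 if more than 6 foods), then up to 4 weeks. 40 + 6 + 4 = 50 weeks, which agrees with the stated maximum; with the extension, 40 + 8 + 4 = 52. In days, 280 + 42 + 28 = 350 and 280 + 56 + 28 = 364.

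Off-challenge days = Exit days - (foods x days per food). The documents do not fix the days per food; 1 or 2 is assumed.

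| Exit length | Foods | Days per food | Off-challenge days | Share of maximum treatment days |
|---|---|---|---|---|
| 42 | 1 | 1 | 41 | 41/350 = 11.7% |
| 42 | 6 | 2 | 30 | 30/350 = 8.6% |
| 56 | 7 | 1 | 49 | 49/364 = 13.5% |
| 56 | 15 | 2 | 26 | 26/364 = 7.1% |

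The range is about 7-13%. EOT is 28/350 = 8.0% or 28/364 = 7.7%. All period lengths are maxima, and extra withheld days would lower the number of off-challenge dosing days.

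**The case against.** The strongest reply is that other outputs already carry most of this information. Every AE leading to epinephrine is an AESI (SAP 7.9.1). AESIs are tabulated by category and by study period. Anaphylaxis of CoFAR grade 3 or higher and 4 or higher appears in all AESI tables. Exposure-adjusted rates of drug-related AESIs count events per person-year and per dose. An epinephrine-treated home-dose reaction between challenges is treatment-emergent and enters these tables. SAP 7.8.3.8 counts accidental exposures needing epinephrine. Epinephrine use is also an exploratory endpoint added in the SAP, and the table shells are in a separate document.

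This largely stands, and it rules out several stronger readings that a reader might infer:

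- **That severe reactions are under-reported.** Severity is graded by CoFAR, not by injection count. What is lost is doses per reaction.
- **That both tables omit EOT.** SAP 7.8.3.6 names EOT twice.
- **That off-challenge use is credited to the food challenge.** The wording on Exit challenges may mean challenge days only, in which case the use is left out. The SAP does not settle it.
- **That about a fifth of blinded treatment time is missing.** That figure adds an Exit gap in one table to an EOT gap in another, and it counts challenge days, which do have a row.

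The reply does not close the gap completely. None of the specified tables shows doses per reaction. The listed by-period AESI tables are by SOC and PT or by PT, and none crosses epinephrine use with prompting event for off-challenge Exit days. SAP 7.9 does not say which AE summaries get the split. Listings are not summaries.

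**Conclusion.** The point holds as three limited defects in descriptive safety output:

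1. The uses-per-subject table and plot in SAP 7.8.3.6 show days with use, not doses per reaction. The effect on the number of subjects with any use is zero.
2. Dosing-related epinephrine on off-challenge Exit days has no stated row and no prompting-event or severity breakdown in 7.8.3.6, and it is not separated in 7.6. The window is about 7-13% of maximum treatment days, resting on the assumed 1-2 days per challenged food.
3. The by-period rescue list in 7.6 omits EOT, about 8% of maximum treatment time. EOT rescue remains in the overall summary and listings.

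The documents do not show that ADP101 harm would be understated overall, because the AESI and CoFAR tables still capture the events. The primary analysis is not affected. The change is worth making because, if the stated period lists are followed, the one table that reports epinephrine by cause leaves out part of blinded dosing, and the SAP already has the split that would fill it.

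**What to change.** In SAP 7.8.3.6:

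- Keep the per-day count, labeled as days with use. Add the number and percent of subjects with any episode treated with 1, 2, or 3 or more doses.
- Apply the during/off-challenge split from SAP 6.4.3 to the Exit period, and extend the prompting-event and maximum-severity breakdown to off-challenge Exit days.

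In SAP 7.6:

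- Apply the same split to the Exit period, and add EOT to the period list.

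The cost is SAP and shell wording, a few more table rows, and linking same-day doses to their AE. SAP 7.8.3.6 already draws on both the concomitant-medication and AE records, and its same-day rule presupposes that separate uses within a day are recorded. The eCRF is not in the documents, so confirm this before the shells are changed. The change concerns counting and tabulation only, not how reactions are treated.
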